VHA Utilization and Costs: VA utilization will be obtained from the national automated datasets maintained at the Austin Automation Center. The VHA Medical SAS Datasets are national administrative data for VHA-provided health care utilized primarily by Veterans. The datasets are provided in SAS format by fiscal year (Oct. 1 - Sept. 30). These data are extracted from the National Patient Care Database (NPCD). Two particular datasets will be used: the “Bed Section” dataset for acute and extended (nursing home) utilization. The “Bed Section” files (as opposed to the Main files) will allow us to differentiate between acute hospitalizations and inpatient rehabilitation, which is necessary for the creation of the Residential History File (see below) as well. These datasets will be used to obtain specific dates of admission and discharge that will enable us to define study outcomes. They also contain variables describing patient demographics, primary/secondary diagnosis, length-of-stay and up to 10 diagnostic code variables per admission. In conjunction with [name] and staff at HERC (Health Economic & Resource Center) we will use HERC cost data based upon standardized cost accounting rules.

Medicare Claims: Medicare data for Veterans are available to VA researchers with approved projects. The VA Information Resource Center, VIREC, prepares the data and attaches it to VA's Scrambled Social Security Numbers, which allows researchers to link VA and Medicare healthcare utilization data. The data are distributed to VA researchers as SAS datasets. The VIREC cohort, first
Version 14: 06/28/17 VA Central IRB Protocol Page 5 of 43
Amendment 15

constructed for 1999, included a total of 6.4 million Veterans. Of these, there were approximately 6.1 million Veterans who were alive as of January 1, 1999. This cohort definition is updated annually to include the most recent source files to produce a cumulative finder file. Currently, files include claims from 1999 through 2011, and are updated continually.

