The following criteria will be considered in creating the matched CLCs for this project. We will match CLCs based upon historical rates of hospitalization from CLC, the proportion of their Veterans who are short, post-acute care patients and the geographic proximity of the CLC to the VAMC inpatient unit. Additionally we will rely on two main types of characteristics: the monthly count of patient days alive in a CLC and the monthly re-hospitalization rate for each CLC. We restricted the analysis to 64 VA CLCs that had at least 50 beds, and were in operation during 2012. In addition, to calculate the matches we will only use data from 12/2007 to 12/2012.

The matching was accomplished in two stages. In the first stage, we partitioned CLCs into 10 groups using k-means clustering, based on the pattern of the monthly number of patient days alive in each CLC. The number of clusters (10) was chosen based on a change in the sum of squared error (SSE) of the scree plot. This step ensured that all of the CLCs within a cluster will have similar number of patient days alive which also corresponds to the size of the CLC. In the second stage CLCs were matched within each of the clusters defined in step 1, based on the monthly re-hospitalization rates per days alive. The matching algorithm within each cluster is of the greedy type that searches for the pair of CLCs with the smallest Euclidean distance, which is calculated based on the re-hospitalization rates in the last five years. Once two of these CLCs are declared to be a “match”, they are removed from further consideration. The algorithm continues to find the closest pair remaining, and removes from consideration once identified. The process continues until all possible CLCs are matched. This two stage process ensures that matched CLCs have relatively similar sizes as well as other characteristics including relatively similar historical re-hospitalization rates.

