We will test the effect of INTERACT on the rate of hospitalization from CLCs taking advantage of *both* the paired control CLCs as well as the differences in the hospitalization rates among intervention facilities before and after the implementation of the intervention. The primary outcome variable is the monthly rate of hospitalization, which, after adjusting for seasonality and trends in the rate over several years prior to the intervention, is compared to the rate of the paired comparison CLC. To allow for regional differences in seasonality, separate ARIMA models will be run for each CLC and then we will use the monthly difference between the observed to the expected CLC hospitalization rate value to compare between the two matched CLCs, aggregating these differences overall pairs. Technically, the average monthly rate of hospitalization before the intervention will be compared to the average monthly rate after and the difference between these two rates will be compared to the differences in the rates of the comparison facilities, using a standard *difference in difference* design.

A similar approach will be used with the person level, risk adjusted hospitalization rates for short and long stay residents calibrated as an annualized rate and there will be fewer facility years than were facility months under the approach described above. The unit of analysis will be the CLC resident but the standard errors will be clustered at the facility level.

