Aim #5: *To conduct a Budget Impact Analysis (BIA) of the INTERACT program from a VA perspective, using the 2-year study follow-up period as the time horizon. Given the important public policy implications for Medicare, we will conduct a secondary BIA from the perspective of the entire Federal Government. The purpose of the BIA is to provide VA managers with the budget impact information they need to manage the start-up and implementation of the program if this project demonstrates that INTERACT works in VA. Preliminary non-VA studies have found INTERACT to save more than 15 times the cost of the intervention. Thus, even if INTERACT is less effective in VA, it still should yield significant savings.*

The BIA will be driven by the other Aims' estimates of the VA effectiveness of INTERACT. As part of the intervention, we will carefully track both the start-up and on-going labor associated with INTERACT. Actual VA labor costs will be used to value this time. The cost savings of the program are not directly observed as they are the hospitalizations that INTERACT prevents, and thus must be estimated. We will obtain data on all VA and Medicare hospitalizations and other types of care. VA costs will be obtained from the DSS fee-basis files, and the Medicare reimbursement will be used as the estimated costs of non-VA care. The first analysis will be to compare the hospitalization costs between the intervention and control sites, including looking for offset effects for other types of care (reduced hospitalizations being partially offset by higher costs for other types of care, including higher costs in the CLC).

We will conduct a full sensitivity analysis of the estimated savings, of how quickly they accrue, and of potential off-setting cost increases. The extent of the savings will be driven by how the intervention affects both the rate of hospitalization, and of the types of hospitalizations (costs vary significantly by the types of conditions treated). Another concern is that the DSS cost estimates include fully allocated overhead costs. The details in the DSS cost data will be used to provide information about how the potential cost savings are distributed across variable direct care costs (e.g., supplies and nursing labor), costs that can only be changed over time (e.g., reallocation of space to other types of care), and allocated overhead costs that will not change with the program.

Statistical Considerations:

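### Aim 5 names no pre-INTERACT cost period for its site cost comparison, so with as few as 8 pairs chance differences in site cost can be counted as savings or losses

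*Combined protocol and SAP*

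**What the plan says.** All references are to the combined protocol and SAP.

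- **Aim #5, cost contrast.** "The first analysis will be to compare the hospitalization costs between the intervention and control sites", including a search for offsets in other types of care and in the CLC itself. The analysis is framed "using the 2-year study follow-up period as the time horizon". No pre-period, baseline covariate or paired estimator is given for cost.
- **Aim #5, source of the effect.** "The BIA will be driven by the other Aims' estimates of the VA effectiveness of INTERACT". The section adds that savings depend on both how many hospitalizations occur and which types, since cost varies by condition.
- **Aim #4, rates.** Each intervention site's mean monthly rate is contrasted pre and post, and this change is then set against that of the controls: "the difference between these two rates will be compared to the differences in the rates of the comparison facilities". Aim #4 calls this a difference-in-difference design. The Study Procedures overview sets the windows at two years before and two years after introduction.
- **CLC Selection, Matching and Random Assignment.** CLCs were clustered on monthly patient days and then matched "based on the monthly re-hospitalization rates per days alive". The overview and this section also list proximity to the VAMC, admissions per bed and the short/long-stay mix. Cost appears in neither list.
- **Cost source.** Data Sources (VHA Utilization and Costs) says "we will use HERC cost data based upon standardized cost accounting rules". Aim #5 takes VA costs from DSS files and values non-VA care at Medicare reimbursement.

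**The concern.** The outcome on which the pairs were matched gets a baseline in the analysis. Cost, on which they were not matched, has none stated. The documents themselves point to reasons why sites may differ in cost: condition mix, allocated overhead in the DSS figures (both Aim #5), and the share of stays outside VA. Preliminary Studies puts that share at 7% overall, but from virtually none to nearly 50% across CLCs, and those stays are valued differently.

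The Aim 4 effect fills only part of the gap. It supplies a baseline-adjusted number of hospitalizations. It does not supply a change in cost per stay, in case type or in offsetting care, and for these the site contrast is the only estimator stated. The plan does not say how the contrast and the Aim 4 effect are combined, so the two could disagree with no rule for resolving it. At stake is the savings figure meant for VA managers.

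**Working it through.** The documents give no cost variance, power or precision figure for this comparison, so there is nothing to reproduce. The steps below show what the omission could do under stated assumptions.

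**Inputs from the documents:** 8 pairs expected as a minimum, up to 15; 20% expected reduction in hospitalizations, applied here to cost.

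**Assumed inputs:** between-site SD of hospitalization cost per resident-day 15–25%; within-pair correlation 0–0.5; pre/post correlation *r* of paired cost differences 0.7–0.9; within-pair SD *s* of the relative cost difference 10–40%. The first two imply *s* = SD × √(2(1 − r_pair)), from 15% × √1 = 15% to 25% × √2 ≈ 35%.

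**1. Effect of a baseline difference.** Let *b* be the intervention sites' relative baseline cost difference and *e* the true reduction. A comparison of follow-up costs alone shows a saving of 1 − (1 + b)(1 − e).
- e = 20%, b = −10%: 1 − 0.9 × 0.8 = 28%.
- e = 20%, b = +10%: 1 − 1.1 × 0.8 = 12%.
- e = 0, b = −10%: 1 − 0.9 × 1 = 10%, a saving where there is none.

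Measured against the sites' own baseline, with no other trend, the answers are 20%, 20% and 0.

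**2. Chance of such a difference.** The SE of the mean baseline difference over J pairs is s/√J (normal approximation).

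| J | s | SE | P(absolute difference > 10%) |
|---|---|---|---|
| 8 | 10% | 3.5% | 0.5% |
| 8 | 20% | 7.1% | 16% |
| 8 | 30% | 10.6% | 35% |
| 8 | 40% | 14.1% | 48% |
| 15 | 20% | 5.2% | 5% |

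For J = 8 and s = 20%: 0.10/0.0707 = 1.41, two-sided probability 0.157.

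**3. Precision with 8 pairs.** Half-width = multiplier × √(2(1 − r_pair)) × SD/√8; for difference in difference, multiply again by √(2(1 − r)).
- Follow-up only, multiplier 1.96: from 1.96 × 1 × 15%/2.83 = 10% to 1.96 × 1.41 × 25%/2.83 = 25%.
- Difference in difference, multiplier 1.96: from 10.4% × √0.2 = 5% to 24.5% × √0.6 = 19%.
- With t on 7 df (2.365), the ranges become about 13–30% and 6–23%.

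**4. When adjustment helps.** Variance relative to follow-up only is 2(1 − r) for difference in difference and 1 − r² for ANCOVA on baseline cost.

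| r | Difference in difference | ANCOVA |
|---|---|---|
| 0.3 | 1.4 | 0.91 |
| 0.5 | 1.0 | 0.75 |
| 0.7 | 0.6 | 0.51 |
| 0.9 | 0.2 | 0.19 |

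Difference in difference gains precision only if r exceeds 0.5. ANCOVA gains for any r other than 0, before allowing for the degree of freedom it uses.

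**The case against.** The strongest reply is that the plan is silent on a cost baseline and does not reject one. A reader might infer that it commits to a follow-up-only comparison; the text does not say so. The quoted sentence says which sites are compared, not by what estimator. Risks to Subjects covers health data for 2008 through 2017, and the Personnel section wants the impact-analysis files to serve the budget analysis too. Part of the document was not available, so absence is judged on the rest. All this stands, but having pre-period data is not the same as specifying its use.

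A reader might also infer systematic bias. The design does not support that. One member of each pair is selected at random and both are dropped on refusal, as they are if a poorly engaged site is later removed, so the expected cost difference is zero. This assumes that acceptance and retention are unrelated to a site's cost relative to its partner, on which the documents are silent.

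Nor does it follow that the savings figure must be contaminated. The analysis is said to rest on the other Aims' estimates, and the Aim 4 effect is baseline-adjusted. That protects the part of the savings that comes from fewer stays, but not cost per stay, case type or offsets.

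Two further points reduce the size. Matching on hospitalization rate controls one component of cost per resident-day, so a within-pair correlation of 0 is a pessimistic bound. Aim 5 also plans to separate overhead from variable costs, although that leaves differences in direct cost per stay.

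Finally, a reader might conclude that DSS must be the primary source because of the overhead split. The documents do not describe HERC's cost detail, so they support only the need to reconcile the two sections.

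**Conclusion.** The point holds as a gap in specification. Aim 5 states a between-site cost comparison over follow-up with no pre-INTERACT cost period, while Aim 4 gives rates a two-year before/after contrast. For cost per stay, case type and offset care, no baseline-adjusted estimate is specified anywhere in the available text.

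The consequence is chance imbalance and lost precision. With 8 pairs and an assumed within-pair SD of 20%, the chance of a baseline difference above 10% is about 16%. It is 0.5% if the SD is 10%, 35% if it is 30%, and 5% with 15 pairs at 20%. These figures illustrate scale; they are not estimates for these sites. Adjustment does not guarantee a precise answer either: with t-based intervals, the upper end for difference in difference (about 23%) still exceeds the 20% effect.

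The primary outcome is unaffected. The estimator should nevertheless be settled before the budget analysis is run, because its result is intended for management decisions.

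**What to change.** 1. In Aim 5, specify that hospital cost and each offset category, per resident-day, are estimated with a paired analysis adjusted for the same sites' costs in the 24 months before introduction. Use either ANCOVA on baseline cost or difference in difference as in Aim 4, chosen in advance, with the same windows and start date as the rate analysis.
2. Base intervals on t with degrees of freedom from the number of pairs: 7 for difference in difference with 8 pairs, 6 for ANCOVA with one baseline covariate.
3. State how the cost result combines with the Aim 4 rate effect, and which figure is the headline saving if they disagree.
4. Reconcile the HERC statement in Data Sources with the DSS statement in Aim 5, so that one primary VA cost source serves both arms and both periods. The other can be a sensitivity analysis.

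The cost is a wording change and extraction of earlier cost records for the same sites, within the 2008–2017 data span already described, plus one degree of freedom if ANCOVA is used. If difference in difference is chosen, precision is lost when the pre/post correlation is below 0.5.

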Significance to the VHA: In conjunction with our GEC partners, this project is being proposed as one component of a general effort to improve care and enhance the medical capacity of CLC nursing and medical staff. If the INTERACT training program is effective, GEC anticipates expanding investment in the on-line training system and identifying local champions at CLCs across the country and implementing INTERACT. The training of CLC nursing and medical staff in INTERACT is completely compatible with, but expands upon, VHA "culture transformation" efforts. Reducing hospitalizations from CLCs has immediate positive benefits on the experience of Veterans since they would be spared the trauma of unnecessary transfer to hospital. In addition, INTERACT training advances several principles central to culture transformation by promoting Veteran-directed advance care planning and training staff to understand Veteran patterns of daily activities to better identify early warning signs and symptoms of decline.

Impact of Findings on the VHA: We expect that, compared to control-CLCs, intervention -CLCs which fully implement INTERACT will reduce hospitalizations by 20%, identifying avoidable hospitalizations. This figure is lower than the 25% reduction in hospitalization among facilities that were engaged in the INTERACT intervention.[11] Consistent with findings from community NHs, these reductions in hospitalizations will be achieved without increasing mortality or accelerating functional decline. From the VAMC perspective, this means hospital beds will be available for more emergent cases without major increases in VHA costs.

C. STUDY PROCEDURES Overview:

The INTERACT program, training curriculum and tools will be refined to be appropriate for implementation in a VA setting both in relation to standard CLC operating procedures and VHA language and policies.

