We estimate our power to detect an expected decrease in hospitalization rate over a 24 month period using simulation analysis, over different scenarios with different sample sizes (# of CLCs), to predict the expected power of our pair matched experiment. Previous research reveals that a Auto-Regressive Moving Average (ARIMA) model characterizes hospitalization rate trends with high accuracy. In our simulations analysis we assume that each CLC’s rate follows an ARMA(2,2) model of the following form:

$$Y_t = c + \epsilon_t + \sum_{i=1}^2 \rho_i Y_{t-i} + \sum_{i=1}^2 \theta_i \epsilon_{t-i}$$
, where ρ_i the correlation of the current to the previous i months, θ_i is the parameter that describe the effect of the error at time $t-1$ on the current hospitalization rate, ϵ_t is normal random with mean zero and standard deviation of σ_ϵ and c is the overall expected hospitalization rate. The simulation analysis included 5 parameters: 1) the sample size in the treatment group; 2) an increase/decrease in the hospitalization rate variance σ_ϵ (F); 3) the size of the effect (c); 4) the accuracy of the decrease $\sigma_{c.}$; and, 5) the variability of ρ_i , θ_i of the nursing home that received treatment from the matched nursing home that received control σ_d . For each configuration of the five parameters, the following algorithm was repeated for 100 times: 1. a sample of n yearly hospitalization rates was chosen from currently observed empirical hospitalization rates and assigned to treatment and control CLCs; 2. sample ρ_i 's, θ_i 's from the above ARMA(2,2) model randomly generated for each of n treatment CLCs; 3. for each i treated nursing home we perturbed the ρ_i 's, θ_i 's by a factor of σ_d , and assigned them to the pair matched control CLC; 4. generate $2n$ ARMA processes using the ρ_i 's, θ_i 's generated in step 2 and 3, and the variance σ_ϵ/F ; 5. decrease the hospitalization rate in the treated group gradually by 5c% to 20c% over 24 months + random deviation of σ_c ; 6. calculate the monthly differences between the treated nursing home hospitalization rate to its matched control, and average across 24 months (τ_j) and calculate the standard error σ_{τ_j} ; and finally, 7. use the average and variance

$$\frac{\sum_{j=1}^J \frac{\tau_j}{\sigma_{\tau_j}}}{\sum_{j=1}^J \frac{1}{\sigma_{\tau_j}}} \text{ and its pooled variance } \left(\sum_{j=1}^J \frac{1}{\sigma_{\tau_j}^2} \right)^{-1}$$

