calculated in 6 to obtain overall weighted average and its pooled variance. To find the factors with the largest effect on power, we calculated the MSE of all the main effects and their interactions. The F, n and c are factors that capture 93% of the variability in the data. Figure 1 shows how the # of CLCs and F (variance of hospitalization rate) affect the power of our analysis. . Even if the monthly reduction in hospital rate will be as low as 10%, using 8 treatment CLCs will result in .77% power.

Figure 4: Power Estimates, Number of CLC’s by Effect Size and Variance in Monthly Hospitalization Rates

Effect	20% Reduction in Hosp. Rate	10% Reduction in Hosp. Rate
--------	-----------------------------	-----------------------------

size										
# CLCs	6	7	8	9	10	6	7	8	9	10
.5	1	1	1	1	1	.99	1	1	1	1
1.0	.98	.99	.99	1	1	.7	.74	.77	.81	.84

Preliminary Studies:

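### The power table reports no zero-effect scenario, alpha or rejection rule, rests on 100 runs per configuration, and uses a printed test that may be anti-conservative

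*Combined protocol and SAP*

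**What the plan says.** Statistical Considerations describes a simulation of matched pairs whose monthly rates follow an ARMA(2,2) process. "For each configuration of the five parameters" (number of treated CLCs, variance factor F, effect size, and two variability terms, sigma_c and sigma_d), "the following algorithm was repeated for 100 times". Each run averages the monthly treated-minus-control differences over 24 months. It then combines the pairs with weights 1/sigma and reports a pooled variance of (sum 1/sigma^2)^-1.

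The power table (labelled Figure 4) has two effect columns, "20% Reduction in Hosp. Rate" and "10% Reduction in Hosp. Rate", for 6 to 10 CLCs and two variance levels. At variance factor 1.0 it gives .98, .99, .99, 1, 1 for the larger effect and .70, .74, .77, .81, .84 for the smaller. The text summarises: "Even if the monthly reduction in hospital rate will be as low as 10" percent, "using 8 treatment CLCs will result in .77% power".

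Of the model equation the section says that "c is the overall expected hospitalization rate". The same letter is also the effect-size parameter. The planned effect, under Impact of Findings on the VHA, is that fully implementing CLCs "will reduce hospitalizations by 20%, identifying avoidable hospitalizations".

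**The concern.** A power figure can be interpreted only if the test rejects at its nominal rate when there is no effect. Here no null scenario is shown, and no alpha, sidedness or rejection rule is given for the primary test. The only alpha in the document, one-tailed .05, belongs to the chart-review sample size under Aim 4. High entries in the table could therefore reflect a sensitive design, or a test that rejects too easily.

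The printed formulas give specific reasons to ask which. The variance does not match the weights, and the data are autocorrelated by construction while the standard error of the 24-month mean is left undefined. If the same statistic were carried into the final analysis, a false-positive finding of benefit would be more likely than the nominal level implies.

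Two smaller matters add to this. One hundred runs give a coarse estimate, and the symbol c carries incompatible meanings.

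**Working it through.** **Reproducing .77.** This is not possible. The document gives symbols but no values for rho, theta, sigma_epsilon, sigma_c or sigma_d, and no alpha. What can be checked is the simulation error and the form of the test.

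**Simulation error, if a cell is one configuration of 100 runs.**
- SE = sqrt(.77 × .23 / 100) = .042, so the 95% half-width is 1.96 × .042 = .082. The exact (Clopper-Pearson) interval for 77/100 is .675 to .848.
- The step from 8 to 10 CLCs is (.84 − .77) / sqrt(.77 × .23/100 + .84 × .16/100) = 1.25 SE, if the cells are independent.
- For .99 (8 CLCs, 20% effect), the exact interval is .946 to .9997.
- If a cell averages k settings of sigma_c and sigma_d, the half-width is 8.2/sqrt(k) points, for example 4.1 for k = 4.

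**Weights and variance.** With J pairs and weights w_j = 1/sigma_j, the variance of the weighted mean is (sum w_j^2 sigma_j^2) / (sum w_j)^2 = J / (sum 1/sigma_j)^2. The printed (sum 1/sigma_j^2)^-1 belongs to weights 1/sigma_j^2. By Cauchy-Schwarz, (sum 1/sigma_j)^2 ≤ J × sum 1/sigma_j^2. The printed variance is therefore never larger than the matching one, and is smaller whenever pair standard errors differ.

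**Autocorrelation.** The difference of two independent ARMA series with the same coefficients has the same autocorrelation as each series. If sigma_j is the ordinary SD/sqrt(24), positive autocorrelation makes it too small. Negative autocorrelation makes it too large.

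**Illustrative null runs of the printed statistic.** All inputs are assumptions: 8 pairs, 24 months, no effect, AR(1) pair differences, SE = SD/sqrt(24), 20,000 runs. The entries are rejection rates at nominal two-sided .05.

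| Lag-1 correlation | Equal pair variances | Pair SDs vary (log-SD .6) |
|---|---|---|
| 0 | 6% | 10% |
| .2 | 13% | 18% |
| .3 | 18% | 24% |
| .5 | 30% | 36% |

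Replacing the pooled variance with J / (sum 1/sigma_j)^2 brought the last column back to about 6%, 13%, 18% and 30%. The mismatch and the autocorrelation are thus separate sources of excess. At correlations of −.2 and −.3 with equal variances, the printed statistic rejected about 3% and 1%.

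**The symbol c.** With c as the intercept, the mean of the printed process is c / (1 − rho1 − rho2), which equals c only if rho1 + rho2 = 0. Step 5 of the algorithm also expresses the reduction as a multiple of c.

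**Precision after a rerun.** With 5,000 runs, SE = sqrt(.77 × .23 / 5000) = .006, a half-width of 1.2 points. For a true 5% null rate the half-width is 1.96 × sqrt(.05 × .95 / 5000) = 0.6 points.

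**The case against.** The strongest reply is that .77 is a deliberately pessimistic case. The planned effect is 20%, where 8 CLCs give .99 and even 6 give .98 (exact lower bound .93), so simulation noise cannot change the design conclusion. This stands as far as noise goes. It does not answer the null question, because an anti-conservative test would raise the .99 as well.

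The 8-point margin may also be too wide. The table shows three of the five parameters, so cells may be averages over the other two. The 10% row lies within .003 of a straight line, smoother than independent 100-run cells would be (probability about .001). Averaging, smoothing or shared random numbers could explain that, and the document does not say which. This too stands, and it is why the interval is stated conditionally.

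Three stronger readings are tempting and not supported:
- **The error rate was never examined.** The document shows only that no check is reported, not what was run.
- **The simulated rates were inflated through c.** That needs code that follows the printed equation literally, observed rates entered as c, and a positive rho1 + rho2. None of these is stated, and a negative sum would reverse the direction.
- **The minimum of 8 CLCs is unsafe because .77 is noisy.** The Study Procedures overview presents 8 as the smallest number expected to accept out of up to 15 approached, and the 20% column covers it against noise.

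Finally, this version is dated June 2017 and the project chart places CLC training in 4/15–8/15. A new table cannot change the sample size. It can still settle the test and its error rate, and correct the stated power.

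**Conclusion.** The point holds as a gap in the justification of power and in the definition of the primary test. No null scenario, alpha, sidedness or rejection rule is reported. The mismatch between weights and variance follows from the printed formulas alone and can only make the test too liberal relative to the matching variance. The effect of autocorrelation depends on its sign and on an unstated standard error. The 6% to 36% null rejection range rests on assumed inputs and shows that a material excess is plausible. It does not show that the sponsor's simulation had one.

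The .77 is known to within .675 to .848 if each cell is one configuration, and more closely if cells are averages. The .99 is secure against simulation noise, but its validity is not established. For c, what is shown is an ambiguous definition; whether it affected the simulation cannot be determined from the documents.

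**What to change.** 1. State the alpha, sidedness and rejection rule for the primary test.
2. Match the pooled variance to the weights: J / (sum 1/sigma_j)^2 for 1/sigma weights, or change the weights to 1/sigma^2. Define a standard error for the 24-month mean that is robust to autocorrelation.
3. Write the model around its mean, (Y_t − mu) = sum rho_i (Y_{t−i} − mu) + error terms, with a separate symbol for the effect.
4. Rerun with at least 5,000 replicates per cell, including a 0% column. State the settings of sigma_c and sigma_d behind each cell.
5. Use the difference-in-difference statistic planned under Aim 4, built on observed-minus-expected rates. The simulation uses raw pair differences, so a 0% column on those would not establish the error rate of the planned test.
6. Replace the table and the power printed as .77% with the new figures.

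The cost is a few hours of computing and possibly a less favourable stated power. The number of CLCs does not change.
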